The imbalance in the microbial equilibrium is termed “dysbiosis”, which has been further defined as a disturbance to gut microbiota homeostasis due to an imbalance in the bacteria itself, changes in their functional composition and metabolic activities. Dysbiosis has been implicated in a wide range of diseases including irritable bowel syndrome (IBS) (**DeGruttola et al.,2016**).

Gut dysbiosis, plays a fundamental role in the pathogenesis of IBS. It was found in IBS patients that gastrointestinal dysbiosis associated with visceral

hypersensitivity, increased gut permeability, mucosal immune activation, chronic inflammation, chronic fatigue, anxiety, and depression (**Wang et al.,2020**).

Irritable bowel syndrome (IBS) is a common functional gastrointestinal disorder, with signs and symptoms including cramping, abdominal pain, bloating, gas, and diarrhea or constipation, or both (**Gupta and Maity, 2021**).

Patients with IBS have shown success with dietary interventions; specifically limiting short-chain carbohydrates known as fermentable oligosaccharides, disaccharides, monosaccharides and polyols (FODMAP). These carbohydrates have shown to be slowly absorbed and highly fermentable, which contributes to the gastrointestinal symptoms. Restriction of FODMAPs has been shown to improve symptoms in 70% of patients with IBS. Diet modifications and exercise combined showed a significant positive improvement in irritable bowel syndrome. (**Sharaf et al.,2021**).

Exercise is a well-established way to alleviate constipation, distension and also for maintaining proper bowel function and reducing stresses. Physical activity improves colonic transit time, gas transit, and bloating by stimulating gastrointestinal motility and most importantly it is becoming more accepted as a safer and effective treatment for irritable bowel syndrome (**Song et al.,2018**).

Exercise can determine changes in the gut microbial composition playing a positive role in energy homeostasis and regulation. Low intensity exercise can influence the gastrointestinal tract reducing the transient stool time and thus the contact time between the pathogens and the gastrointestinal mucus layer . As a consequence, it seems that exercise has protective effects, reducing the risk of colon cancer and inflammatory bowel disease (**Monda et al.,2017**).

Moderate aerobic exercise affects the intestinal system mainly through gut immune function, gut barrier integrity, as well as gut motility, intestinal pH and gut hormones release; and bile acids metabolism within enterohepatic circulation (**Resende et al., 2021**).

Also High-intensity interval training is a popular, time-efficient mode of exercise to improve metabolic health and aerobic fitness, both of which have been associated with healthier gut bacterial community structure (**Rettedal et al., 2020**).

Statement of the Problem:

Is there a significant difference between the effect of moderate continuous versus high interval intensity training on gut dysbiosis and glucagon like peptide hormone in irritable bowel syndrome?

The Purpose of the Study:

To compare the effect of moderate continuous versus high interval intensity training on gut dysbiosis and glucagon like peptide hormone in irritable bowel syndrome.

Significance of the Study:

Irritable bowel syndrome affects around 11% of the global population with variation by geographic region: the highest in South America (21.0%) and the lowest occurring in South Asia (7.0%). In Egypt, the prevalence was 34% in primary healthcare center attendees. IBS significantly reduces work productivity and health-related quality of life (**Mohamed et al.,2021**).

The quality of life for patients suffering from IBS is greatly affected physically, psychologically, and economically. Several cases reported difficulties in concentration, decreased energy level, and lower self-esteem. In-addition IBS is

inducing occupational hazards as it affects the performance of patients at their jobs (**Elsayed et al.,2021**).

Although half of the cases referred to gastroenterologists is due to IBS, no clear etiology was found; however, some researches revealed that certain factors such as psychological factors, dietary habits, and exercise level were related to IBS onset and course (**Elhosseiny et al.,2019**).

Previous studies have been done separately on the effect of moderate intensity continuous training program and high intensity interval training on irritable bowel syndrome and gut dysbiosis, it is rational to compare between two training programs to know which is more effective to improve gut microbiota balance.

Delimitations:

This study will be delimited to the following aspects:

Subjects will be delimited to patients with irritable bowel syndrome selected from the outpatient of national nutrition institute with the following criteria:

- Sixty six patients with irritable bowel syndrome of both genders.
- Their ages ranged from 20 to 45 years.
- Their Body mass index ranged from 30 to 34.9.
- Patients will be divided into 3 groups
 - **Group A:** Patients will receive moderate intensity continues training exercise program along with following Low fermentable, oligosaccharides, disaccharides, monosaccharides and polysaccharides diet plan (FODMAPs diet).
 - **Group B:** Patient will receive high intensity interval training exercise program along with following FODMAP diet plan.

- **Group C:** Patients will follow FODMAP diet plan only.
- Patients will be excluded if:
 - - Uncontrolled hypertension
 - - Gastrointestinal bleeding
 - - Colorectal cancer or any terminal diseases
 - - Communication disorders

Basic Assumptions:

It will be assumed that:

- 1) The primary medical assessment will be done to every participating patient who includes:
- 2) Complete medical history (personal, present and past)
- 3) All patients will stick to the program and will follow instructions.
- 4) All other factors which may influence the outcome such as noise and distraction will be controlled.

Hypothesis:

It will be hypothesized that there will be no significant difference between the moderate continuous versus high interval intensity training on gut dysbiosis and glucagon like peptide hormone in irritable bowel syndrome.

CHAPTER II

REVIEW OF LITERATURE

The human gastrointestinal (GI) tract represents one of the largest organ between the host, environmental factors and antigens in the human body. In an average life time, around 60 tonnes of food pass through the human GI tract, along with an abundance of microorganisms from the environment which impose a huge threat on gut integrity. The collection of bacteria, archaea and eukarya colonising the GI tract is termed the ‘gut microbiota’ and has co-evolved with the host over thousands of years to form an intricate and mutually beneficial relationship (**Thursby and Juge,2017**).

The gut microbiota enjoys a mutualistic relationship with the host, harvesting additional energy and nutrients from the diet and protecting the host from pathogens. The resident bacteria produce a wide range of metabolites and chemicals that influence host function and these include short-chain fatty acids such as butyrate, which is essential for the integrity of the colonic epithelium. However, there is potential for these mechanisms to be disrupted as a result of an altered microbial composition, known as dysbiosis (**Lin and Zhang,2017**).

Human Gut dysbiosis is linked to many pathologic conditions disturbing the energy metabolism; such as obesity and atherosclerosis. The microbiota in the human gut is mostly composed of bacterial phyla: Firmicutes and Bacteroidetes (**Thursby and Juge,2017**).

Firmicutes bacteria are Gram-positive one. It plays a key role in the nutrition and metabolism of the host through SCFA synthesis. Through their metabolic products, Firmicutes bacteria are indirectly connected with other tissues and organs and regulate hunger and satiety. In contrast, Bacteroidetes bacteria are Gram negative and associated with immunomodulation. Increased or decreased

Firmicutes / Bacteroidetes (F/B) ratio are associated with the development of obesity or irritable bowel disease (IBD) (**Stojanov et al.,2020**).

Short-chain fatty acids (SCFAs), the primary metabolite for colonocytes, are produced in the intestinal lumen by commensal anaerobic bacteria via carbohydrate fermentation. They play a role in preserving gut barrier functions, and have immunomodulatory and anti-inflammatory properties also it regulates the synthesis of the hunger-suppressing hormones leptin, peptide YY, and glucagon-like peptide 1. The gut microbiota can also affect appetite and satiety via vagus nerve activation or immune-neuroendocrine mechanisms (**Protincasa et al.,2022**).

Irritable bowel syndrome (IBS) is a common gastrointestinal disorder characterized by chronic abdominal pain and changes in bowel habits without any known organic causes (**Aziz and Simern, 2021**).

Fecal SCFAs abnormalities have been reported in patients with IBS, implying that alterations in SCFAs might be related to IBS. The cause of IBS remains unknown, and no single treatment is found to be universally applicable to all patients with IBS (**Sun et al., 2019**).

Among humans, positive correlations were reported between bacterial diversity, butyrate-producing bacteria and cardiorespiratory fitness (VO₂max), and higher turnover of carbohydrates and proteins, and concentrations of short-chain fatty acids in athletes compared to sedentary controls. There is also growing evidence that physical activity status and exercise training may shape the gut microbiome (**Cataldi et al.,2022**).

Physical activity stimulates bacterial community richness by altering SCFAs-producing species, as well as favoring the colonization of health and athletic performance-promoting strains. The ability to promote a bacterial

composition capable of protecting the intestinal mucosa also it was found that the effects on gut microbiome seem to gradually disappear when the physical activity is no longer practiced (**Cataldi et al., 2022**).

Moderate aerobic exercise affects the intestinal system mainly through gut immune function gut barrier integrity through tight junction proteins expression and IgA production hypothalamic–pituitary–adrenal (HPA) axis stimulation which, in turn, affects enteric nervous system and intestinal transit time, as well as gut motility, intestinal pH and gut hormones release and bile acids metabolism within enterohepatic circulation (**Cella et al.,2021**).

High intensity interval training (HIIT) encompasses exercise prescriptions that are tailored to individual needs and can be used in most any exercise setting. This ability to adapt makes HIIT a valuable tool in the exercise programming of patients with a chronic disease. HIIT has a positive effect on the Bacteroidetes/Firmicutes ratio and also increased the alpha diversity in gut microbiota (**Denou et al.,2016**).

Chapter III

[figure not shown]
PATIENTS, MATERIALS AND METHODS

The current study is designed to compare between the effect of moderate continuous and high interval intensity training on gut dysbiosis and glucagon like peptide hormone in irritable bowel syndrome.

I. Patients:

This study will be carried out on sixty six irritable bowel syndrome patients of both sexes with an age range between twenty to forty five years. Patients will be recruited and practical work of the study will be carried out in national nutrition institute physiotherapy out clinic. Patient will be randomly assigned to three groups.

To avoid type II error, sample size calculation is performed using G*POWER statistical software (version 3.1.9.2; Franz Faul, Universitat Kiel, Germany). To detect a large effect size of 0.4 with power of 80% and $\alpha=0.05$, the required sample size required for this study was $N=66$.

Ethical consideration:

- Approval of faculty ethical committee.
- The study procedure will be explained for all participants.
- Confidentiality will be assured.
- An informed consent will be taken from each subject prior to participation.

(Appendix I)

Criteria for the patient selection:

Inclusion criteria:

- 1) Patients will be selected with age range of 20 to 45 years of both genders.
- 2) Body mass index (BMI) will range from 30 to 34.9 kg\m².
- 3) Having more than one symptom for ROME IV for IBS diagnostic criteria **(Appendix II).**
- 4) Prediabetic with glycated hemoglobin HbA1c of 5.7 – 6.4.
- 5) Sedentary subjects with daily steps count less than five thousand steps measured by pedometer **(Prince et al.,2020).**

Exclusion criteria:

Patients with the following criteria will be excluded from the study:

- 1) Communication disorders
- 2) Gasterointestinal bleeding
- 3) Antibiotics or probiotics in the last 2 months
- 4) Recent surgeries in the last 6 months
- 5) Colorectal cancer or any terminal diseases
- 6) Fibromylgia or Multiple sclerosis
- 7) Palpable abdominal mass
- 8) Cardiovascular diseases

- 9) Active smokers
- 10) Musculoskeletal injuries that interfere with exercise program
- 11) Upper respiratory infections
- 12) Uncontrolled hypertension

Patients will be divided into 3 groups:

- **Group (A):** This group will include 22 patients with IBS. These patients will receive 40 minutes of MICT on the treadmill: 5 minutes of warm-up followed by 30 minutes of 65-75% of target heart rate ending with a 5 min cool-down period for 12 weeks along with following low FODMAP diet plan.
- **Group (B):** This group will include 22 patients with IBS. These patients will receive HIIT sessions consisting of a 30 minutes treadmill session a 5 minutes warm-up followed by 10 bouts of 1 minute at 90% of target heart rate interspersed by 10 bouts of 1 min of active recovery at 50% of target heart rate (totaling 20 min), and a 5 minutes cool-down period for 12 weeks along with following low FODMAP diet plan.
- **Group (C)** This group will include 22 patients with IBS. These patients will follow low FODMAP diet plan for 12 weeks

Materials and Methods

- **Evaluation**

Out comes to be measured:

1) Primary outcomes

- a- Short chain fatty acids via gas chromatography
- b- Glucagon like peptide 1 via Elisa kit

2) Secondary outcomes

- a- Irritable bowel syndrome scoring system

- b- Irritable bowel syndrome quality of life questionnaire (IBS QoL)
- c- Change in body weight via body mass index (BMI)

Evaluation equipment and tools:

a) Gas chromatography: SCFAs butyrate and acetate

For SCFA analyses, fecal sample will be separated. Applying four analytes, including total SCFAs, acetate, propionate, and butyrate, will be targeted. Final concentrations will be calculated based on internal standards and are expressed as micromoles per gram of wet feces ($\mu\text{mol/g}$). Techniques and predictive approaches will be used across. gas chromatography will be used to quantify Short Chain Fatty Acids (SCFAs) from fecal samples (**Chen et al.,2021**).

b) Elisa Kit for serum GLP 1 hormone

This kit is an Enzyme-Linked Immunosorbent Assay (ELISA). The plate will be pre-coated with Human GLP-1 antibody (**Kuhre et al.,2015**).

c) Weight and Height measurements

Weight and height will be recorded to calculate body mass index (BMI) according to the following equation: (**Shukohifar et al.,2022**)

$$\text{BMI} = \text{weight}/\text{height}^2 \text{ (Kg/m}^2\text{)}.$$

d) IBS severity scoring system (Appendix III)

This five-item questionnaire will measure IBS symptom severity by addressing abdominal pain (frequency and severity), bloating, dissatisfaction with bowel habits, and interference with daily activities. Each question score ranges from 0 to 100 and a higher score indicates more severe GI symptoms. A total score of 75–175 represents mild IBS, 176–300 moderate IBS and >300 severe IBS (**Zeid et al.,2020**).

e) Irritable bowel syndrome quality of life questionnaire (IBS QoL) (Appendix IV)

The IBS-QoL is a condition-specific instrument will be used to assess the impact of IBS and effects of treatment. It consists of 34 questions which cover eight domains including dysphoria, interference with activity, body image, health worry, food avoidance, social reaction, sexual, and relationships. Each item has a five-point response scale (not at all, slightly, moderately, quite a bit, extremely). The responses are summed and averaged for a total score and transformed to a scale between 0 and 100: higher scores indicating better IBS-specific QoL (Hou et al.,2015).

3-Management procedure:

After collecting the consent forms, will be examined by the researcher for the inclusion and exclusion criteria. Each eligible patient (according to the consent form and examination) will participate in the study.

Group A

Patients will receive moderate intensity continuous training (MICT).

The program will be in form of: (Clark et al.,2020).

- **Frequency:** Moderate continues training will be scheduled 3 times per week for 12 weeks
- **Intensity:** 65-75% of target heart rate.
- **Duration:** 40 minutes per session. Patients will be instructed to follow low fermentable short chain carbohydrates diet (low FODMAP) intervention for 12 weeks limiting daily fermented carbohydrate and dairy products intake and increase intake of protein, whole grains, fruits and vegetables

(Appendix V)

- **Group B**

Patients will receive high intensity interval training (HIIT)

The program will be in form of: **(Clark et al.,2020).**

- **Frequency:** High intensity interval training will be scheduled 3 times per week for 12 weeks
- **Intensity:** 90% of target heart rate including 10 bouts of 1 minute interspersed with 10 bouts of 1 minute of active recovery 50% of target heart rate.
- **Duration:** the session will last 30 minutes includes warming up and cooling down periods

Patients will be instructed to follow low fermentable short chain carbohydrates diet (low FODMAP) intervention for 12 weeks limiting daily fermented carbohydrate and dairy products and increase intake of protein, whole grains, fruits and vegetables

Group C

Patients will be instructed to follow low fermentable short chain carbohydrates diet (low FODMAP) intervention for 12 weeks limiting daily fermented carbohydrate and dairy products and increase intake of protein, whole grains, fruits and vegetables **(Vareny et al.,2017).**

Only the patients who will attend > 80% of the exercise training sessions will be included in this study.

Data Analysis and statistical design

- The collected data was analyzed using the statistical program SPSS ver. 20.0.
- The mean and standard deviation were calculated for all measured variables.
- Pearson correlation coefficient was used to determine the relationship between the measured variables.
- Statistical significance was set at $p < 0.05$.

REFERENCES

Aziz I & Simrén M (2021). The overlap between irritable bowel syndrome and organic gastrointestinal diseases. *The Lancet Gastroenterology & Hepatology*, 6(2), 139–148.

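### The randomised diet-only arm (Group C, 22 of 66) has no role in the stated purpose, hypothesis or analysis, so the plan prespecifies no contrast that shows whether either training adds to the diet

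*Combined protocol and SAP*

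**What the plan says.** The section on the purpose of the study gives the aim as "To compare the effect of moderate continuous versus high interval intensity training on gut dysbiosis and glucagon like peptide hormone in irritable bowel syndrome". The statement of the problem, the hypothesis (a null of no difference between the two trainings) and the opening sentence of Chapter III have the same scope. The significance section justifies the trial on the ground that "it is rational to compare between two training programs to know which is more effective to improve gut microbiota balance".

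The design has a third arm. Chapter III states that "Patient will be randomly assigned to three groups", each of 22. In Group C, according to the delimitations, "Patients will follow FODMAP diet plan only". Groups A and B follow the same diet for the same 12 weeks, plus MICT or HIIT. Group C appears only where groups are allocated and managed; no sentence says what it is to be compared with.

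The sample-size paragraph reads "To detect a large effect size of 0.4 with power of 80" percent and concludes that "the required sample size required for this study was $N=66". It names neither the test nor the effect-size metric. The data analysis section lists means, standard deviations, Pearson correlation and a 0.05 significance level. It names no A–C, B–C or three-group test. The management section also restricts inclusion to patients who attend more than 80% of exercise sessions.

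**The concern.** All three arms start an active diet at the same time, and the plan itself makes that diet a serious rival explanation for improvement. The introduction says of symptoms that "Restriction of FODMAPs has been shown to improve symptoms in 70% of patients with IBS". The literature review describes short-chain fatty acids as products of carbohydrate fermentation that regulate GLP-1 synthesis, so a diet limiting fermentable carbohydrate acts on the pathway to both primary outcomes. The plan gives no size for that effect, and it could imitate a training effect or hide one.

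The stated hypothesis is that A and B do not differ. If it is not rejected and both arms improve, the natural sentence in the report is that the trainings are similarly effective. The stated question offers no check on that sentence. The arm that could check it has been randomised and followed, but any use of it would be unplanned.

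**Working it through.** **Inputs.** From Chapter III: N = 66, three groups of 22, effect size 0.4, power 80%, alpha 0.05. Assumptions, because the plan is silent: 0.4 is Cohen's f, pairwise tests are two-sided, SDs are equal across arms, and there is no dropout.

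**1. Reproduce the plan's figure.** One-way ANOVA, noncentral F with λ = N·f².
- Three groups, N = 66: λ = 66 × 0.16 = 10.56 on 2 and 63 df, power 0.818. The smallest N reaching 80% is 64 (power 0.805; N = 63 gives 0.798), which becomes 66 with equal groups.
- Two groups, f = 0.4: N = 52 (power 0.807).
- Two means, normal approximation: d = 0.4 needs 99 per arm, d = 0.8 needs 25 per arm.

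Of these readings only the three-group one gives 66. The sizing therefore appears to include Group C, although the purpose and hypothesis do not.

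**2. What each contrast identifies.** Let D be the mean change in Group C (diet, time and regression to the mean together), and write the mean changes in A and B as D + a and D + b.
- A − B = a − b. D cancels, so the shared diet does not bias this contrast.
- A − C = a and B − C = b.
- The before–after change in A is D + a, which does not identify a.

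If a = b = 0, then A − B = 0. If a = b and both are large, A − B is again 0. In both cases A and B improve whenever D is favourable. Only A − C and B − C tell the two apart. A significant three-group F-test alone would not say which arms differ.

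**3. What f = 0.4 means for training versus diet.** If A and B are equal and both differ from C by m SD, the means are (m, m, 0) and the grand mean is 2m/3. The between-group variance is [2(m/3)² + (2m/3)²]/3 = 2m²/9. Hence f = m√2/3 and m = 0.4 × 3/√2 = 0.85.

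**4. Power of A–C and B–C at 22 per arm.** The noncentrality is d√(n/2) = 0.85 × √11 ≈ 2.8.

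| Alpha per contrast | Power, d = 0.85 | Per arm for 80% | Total |
|---|---|---|---|
| 0.05 (unadjusted) | about 79% | 23 | 69 |
| 0.025 (Bonferroni, 2 contrasts) | about 70% | 28 | 84 |
| 0.0167 (Bonferroni, 3 contrasts) | about 64% | 31 | 93 |

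By simulation, when both trainings truly differ from C by 0.85 SD, both unadjusted contrasts are significant about 67% of the time. In about 23% exactly one is, although the trainings are equal.

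**5. What a non-significant A–B shows.** For a true A–B difference of 0.5 SD, the noncentrality is 0.5 × √11 = 1.66 and power is about 37%, so the difference is missed about 63% of the time. The 95% interval for A–B has a half-width of about 2.00 × √(2/22) = 0.60 SD before baseline adjustment.

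**The case against.** The stated question is comparative, and randomisation with a common diet answers it without bias. That stands: the A–B contrast needs no repair on account of the diet. Group C is also randomised and concurrent, so the control for diet is already in the design. The fault lies in the objectives and the analysis text.

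A reader might infer that the trial will report A–B alone and ignore Group C. The documents do not say so. The analysis section promises descriptive statistics for all measured variables, names no between-group test even for A–B, and the sample size fits three groups. What can be said is that the role of Group C is unstated.

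A reader might also take the 70% as the share of each exercise arm that improves from diet alone, and so as a ceiling on what training can add. That does not follow. The figure concerns symptoms, a secondary outcome here, and the plan does not say whether it is net of a control. Symptom severity is scored continuously with no responder definition, so a patient who improves on diet can improve further with training. No diet effect on SCFA or GLP-1 is given.

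Finally, the missing between-group test could be called the more basic fault. Naming a test for the hypothesis as written would still leave Group C out, so this point stands separately.

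**Conclusion.** The point holds and should be corrected before the data are analysed. As written, the plan draws no prespecified conclusion from 22 of 66 patients (33%), and a finding of no A–B difference could not show whether either training adds to the diet. A later report could still add A–C and B–C, but those contrasts would be post hoc.

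The point does not extend to bias in A–B, and it puts no number on how much improvement the diet produces; the documents support neither. The statement that the sizing counts Group C rests on reading 0.4 as Cohen's f. The power figures rest on the pattern in which A and B are equal and both differ from C by 0.85 SD, with no dropout. A smaller benefit over diet would be detected less often: at 0.4 SD, about 25% of the time per contrast, unadjusted.

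**What to change.** - **Purpose and hypothesis.** Add A versus C and B versus C as the contrasts that show whether each training adds to the diet, for SCFA, GLP-1 and the secondary outcomes.
- **Analysis.** Estimate A–C, B–C and A–B in one three-group model adjusted for the baseline value (ANCOVA), with a named multiplicity adjustment across the contrasts.
- **Population.** Use all randomised patients. Group C has no exercise sessions, so the attendance rule can remove patients only from A and B; an attenders-only comparison with C would no longer be fully randomised. It can be kept as a sensitivity analysis.
- **Reading rule.** Credit a training only on its difference from C, never on its own before–after change. Otherwise conclude that no benefit over diet was shown. Report A–B as an estimate with a confidence interval, and do not call the trainings similarly effective because A–B is non-significant.

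The cost is mainly wording, with no new arm, visit or assay, plus the effort to obtain outcomes from low attenders. The claim becomes harder to win. At 22 per arm and 0.85 SD, each contrast has about 79% power unadjusted and 64% to 70% after Bonferroni adjustment, and both are significant only about 67% of the time even unadjusted. The plan should state this, or restate the sample size for these contrasts (84 to 93 in total with adjustment, before dropout). Baseline adjustment would recover some power, but the documents give no baseline correlation from which to say how much.

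### The stated 80% power is tied to no comparison; for MICT versus HIIT at 22 per arm it needs a difference of about 0.86 SD (unadjusted, two-sided 0.05)

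*Combined protocol and SAP*

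**What the plan says.** The sample-size paragraph in Chapter III (I. Patients) gives the software (G*Power), an effect size and a total: "To detect a large effect size of 0.4 with power of 80" per cent, alpha 0.05, N=66. The group descriptions then allot 22 patients to each of three arms: MICT plus diet, HIIT plus diet, and diet only.

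Five places state what the trial is for, and all of them concern the two exercise programmes:

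- Statement of the Problem: "Is there a significant difference between the effect of moderate continuous versus high interval intensity training".
- The Purpose of the Study, in nearly the same terms.
- Significance of the Study: "it is rational to compare between two training programs to know which is more effective to improve gut microbiota balance".
- Hypothesis: "there will be no significant difference between the moderate continuous versus high interval intensity training".
- The opening of Chapter III: the study is "designed to compare between the effect of moderate continuous and high interval intensity training".

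None of them makes a comparison with diet only the aim.

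Data Analysis and statistical design lists means and standard deviations, a significance level of 0.05, and one inferential method: "Pearson correlation coefficient was used to determine the relationship between the measured variables". No between-group test is named there or elsewhere.

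**The concern.** A power figure belongs to a particular test of a particular contrast. Here the 80% belongs to none that the text names. The total fits an omnibus test of three groups, while the question is about two of them. Omnibus power does not transfer to a pair, because the omnibus test can reject on the strength of the diet-only arm alone.

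The paragraph presents the calculation as protection against type II error, yet the plan gives no type II error rate for the comparison it poses. A reader could easily take the 80% as the chance of detecting a difference between the programmes. The hypothesis predicts no significant difference, so a non-significant result from an underpowered comparison could be over-read as showing that the programmes are alike.

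**Working it through.** **Inputs from the protocol.** Effect size 0.4, power 80%, alpha 0.05 and N=66 (I. Patients); three groups of 22 (group descriptions). Sidedness is not stated, so I take two-sided for the pairwise test.

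**1. Reproduce N=66.** For an omnibus F test with k=3 groups and Cohen's f=0.4, the noncentrality is λ = f²N, with df 2 and N−3 (N−4 with one covariate).

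| Balanced total | λ | One-way ANOVA | ANCOVA, one covariate |
|---|---|---|---|
| 63 | 0.16 × 63 = 10.08 | 79.8% | 79.7% |
| 66 | 0.16 × 66 = 10.56 | 81.8% | 81.8% |

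So 66 is the smallest balanced total for either test. Other readings of 0.4 give different totals for 80% power:

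- two-sample t test with d=0.4: 200
- two-group F test with f=0.4 (d=0.8): 52
- paired t test with d=0.4: 52
- correlation r=0.4: about 47
- three groups by two times, assumed within-patient correlation 0.5: 21 for the interaction, 51 for the between-group effect

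Of the readings tried, only the three-group omnibus F test, with or without a covariate, gives 66.

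**2. What f=0.4 implies for MICT versus HIIT.** With equal groups and SD 1, f² = Σ(mean deviation)²/3, so the squared deviations sum to 3 × 0.16 = 0.48. That fixes the overall spread but not which groups differ. For 22 versus 22, the noncentral t has δ = d√(22/2) = d√11. The rates below use df 42, then df 63 (error variance pooled over three groups).

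| Pattern of means, all with f=0.4 | MICT−HIIT difference d | Rejection rate, two-sided 0.05 |
|---|---|---|
| MICT = HIIT, both differ from diet only | 0 | 5.0% / 5.0% |
| Equally spaced, MICT and HIIT adjacent | 0.4√1.5 = 0.49 | 35.5% / 36.0% |
| One exercise arm differs from the other two groups | 0.4 × 3/√2 = 0.85 | 78.5% / 79.1% |
| MICT and HIIT are the extremes | 0.4√6 = 0.98 | 88.8% / 89.2% |

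Omnibus power is 81.8% in every row. The rows are points on a continuous range.

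**3. Detectable difference for the stated question.** Solving for 80% power at 22 per arm gives d = 0.865 (df 42) or 0.858 (df 63), about 0.86 SD. This does not depend on which test produced N=66.

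**4. Sensitivity. None of these conditions is in the plan.**

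| Condition | d for 80% power |
|---|---|
| 20 per arm | 0.91 |
| 18 per arm | 0.96 |
| Alpha 0.025 (split over two primary outcomes) | 0.96 |
| Alpha 0.01 (split over GLP-1 and four SCFA analytes) | 1.07 |
| One-sided 0.05 | 0.76 |
| Baseline adjustment, correlation 0.3 / 0.5 / 0.7 | 0.83 / 0.75 / 0.62 |

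The last row is 0.865 × √(1−r²), with df 41. Losses are relevant because no dropout allowance is stated and the protocol keeps only patients who attend more than 80% of exercise sessions, a rule that bears on the two arms being compared.

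**5. Precision.** The 95% CI half-width is t(0.975, 42) × √(2/22) = 2.018 × 0.3015 = 0.61 SD.

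**The case against.** The arithmetic is not in error. Calling 0.4 large, having three groups and arriving at 66 together point strongly to Cohen's f in an omnibus F test, and powering a three-arm trial that way is common. That stands, and the point is not that 66 was miscalculated. But common practice would follow the omnibus test with planned pairwise comparisons. The plan names neither step, and every statement of aim is pairwise.

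The shortfall also depends on the pattern of means. In two of the four patterns the pairwise rate is 79% or 89%, so the stated 80% is roughly met or exceeded. The 5% in the first pattern is a type I error rate, because there is then no difference to miss. Both remarks are fair. They show that 80% may hold for MICT versus HIIT, but nothing in the documents says that a favourable pattern is expected.

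The 0.86 SD carries conditions: two-sided, unadjusted, nobody lost, alpha not split. A one-sided test or baseline adjustment would lower it, though neither is planned. The 1.07 SD figure is the weakest. Evaluation equipment and tools says "Applying four analytes, including total SCFAs, acetate, propionate, and butyrate, will be targeted", but that item's own heading names only butyrate and acetate, total SCFA overlaps its components, and no document proposes splitting alpha. It is an illustration only.

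Finally, the Hypothesis may be no more than a conventional null. That is possible, and I do not claim that equivalence is intended. The plan simply does not say how a non-significant result will be read.

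**Conclusion.** The concern holds. The stated 80% cannot be attached to MICT versus HIIT, the only comparison the plan poses. Under the inferred omnibus test, the chance of rejecting for that pair runs from 5% to 89% according to a pattern of means the plan does not give. At a true difference of 0.49 SD, which is compatible with f=0.4, the trial would miss it about 64% of the time (100 − 36). For 80% power the difference must be about 0.86 SD, assuming a two-sided 0.05 test, all 22 per arm analysed, no baseline adjustment and no multiplicity adjustment. With an interval reaching 0.61 SD either side of the estimate, a non-significant result would not by itself show that the programmes are alike.

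The omnibus reading is an inference that the sponsor should confirm. The 0.86 SD does not rest on it. The analysis section, followed as written, would not make the comparison at all. This should be fixed, but it does not call the sample size itself into question.

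**What to change.** First ask the sponsor which test, effect-size metric and outcome were entered in G*Power. Then restate the sample-size paragraph, for example:

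> N=66 (22 per group) gives 82% power for a three-group omnibus F test at f=0.4. For MICT versus HIIT, with all 22 per arm analysed in an unadjusted two-sided test at 0.05, power is 80% only for a difference of about 0.86 SD. Power is lower if patients are lost or alpha is split over several primary outcomes or analytes; a smaller difference is detectable if baseline adjustment reduces residual variance.

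If another test was used, only the first sentence changes.

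In Data Analysis and statistical design, add:

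> MICT and HIIT will be compared between groups for each primary outcome, and the difference reported as an estimate with a 95% CI. Comparisons with diet only will also be reported. A non-significant result will not by itself be taken as evidence that the two programmes are alike.

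The cost is text in two sections and a little more analysis, with no extra patients. The downsides for the sponsor are a less favourable stated power figure and a commitment to a between-group comparison.
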